2.7.2 Statistical hypothesis, model, and method of analysis

Number of new or enlarging T2 lesions on MRI scans

Analysis of the number of new or enlarging T2 lesions will be done based on the FAS using a negative binomial regression model with log-link. The number of new or enlarging T2 lesions on the last available MRI scan relative to baseline will be used as the response variable, and the natural log of the time (in years) of the MRI-assessment from the baseline/Screening scan will serve as the offset variable to adjust for the various lengths of follow-up times between patients in this study. The model will include treatment, region (Japan or other countries), baseline number of Gd-enhancing T1 lesions (0 or ≥ 1) as factors, and baseline volume of T2 lesions as continuous covariates.

The number of new or enlarging T2 lesions per year will be estimated by treatment with 95% confidence interval. The between treatment effect will be calculated as rate-ratio (ofatumumab/placebo) with 95% confidence interval and p-value. In addition, the relative reduction in the number of new or enlarging T2 lesions per year will be computed as one (1) minus the rate-ratio and expressed as a percentage.

The number of new or enlarging T2 lesions on MRI scans will be summarized descriptively by visit-window and treatment group.

The above summary analyses will be performed for both Cut-off 1 analysis and Cut-off 2 analysis ([Section 2.14](#)).

Annualized relapse rate (ARR)

Annualized relapse rate (ARR) is defined as the number of confirmed MS relapses in a year. Analysis of ARR will be done based on the FAS, using a negative binomial regression model with log-link. The model will include the number of confirmed relapses observed from each patient as the response variable, each patient's natural log of time in study (years) as the offset variable, and treatment, region (Japan or other countries), baseline number of Gd-enhancing T1 lesions (0 or ≥ 1) as factors, and number of relapses in previous year and baseline EDSS as covariates.

In the case where the above model does not converge or has other statistical limitations, a simpler model with only the offset variables, treatment and region (Japan or other countries) as factors will be fit to the data.

The adjusted ARR (i.e., model-based estimate adjusted for covariates) for each treatment and the corresponding 95% confidence interval, and ARR ratio (also expressed as percentage reduction relative to control group) along with the 95% confidence interval for the ARR ratio and the corresponding p-value will be obtained.

The definition of a confirmed MS relapse is one accompanied by a clinically relevant change in the EDSS assessment, i.e. an increase of at least 0.5 points on the EDSS (total) score, or an increase of at least 1 point on at least two Functional scores (FSs), or an increase of at least 2 point on at least one FS, excluding changes involving bowel/bladder or cerebral FS, compared to the last EDSS assessment taken in the absence of (confirmed or unconfirmed) relapse and prior to the current relapse. EDSS obtained on the date as indicated on the Summary of MS

Relapse eCRF page will be used. If such EDSS assessment is missing or not meeting the criteria to confirm the relapse, all other EDSS assessment taken within 30 days from the relapse start date (i.e., EDSS assessment date – relapse start date ≤ 30) and before the relapse end date (EDSS assessment date \leq relapse end date) will be checked. If at least one of such available EDSS assessments meets the criteria, the relapse is a confirmed one. Otherwise, the relapse is considered an unconfirmed one.

The patient's time in study for ARR at each cutoff will be calculated as (Cutoff point – first dose date + 1)/365.25.

The analysis will be performed at Cut-off 1 analysis. The adjusted ARR for each treatment and the corresponding 95% confidence interval will be provided also for Cut-off 2 analysis ([Section 2.14](#)).

Time to first confirmed relapse

Time to first confirmed relapse will be calculated as (start date of first confirmed relapse – date of first administration of study drug + 1). For patients without confirmed relapses at a cutoff point, they are censored with censoring time as time in study at the corresponding cutoff point.

Analysis of time to first relapse will be done based on the FAS, using a Cox proportional hazard model with treatment, region (Japan or other countries), and baseline number of Gd-enhancing T1 lesions (0 or ≥ 1) as factors, and number of relapses in previous year and baseline EDSS as covariates. The hazard ratio (also expressed as percentage reduction relative to control group) along with the 95% confidence interval for the hazard ratio and the corresponding p-value will be obtained. In the case where the above model does not converge or has other statistical limitations, a simpler model with only treatment and region (Japan or other countries) as factors will be fit to the data. The Cox model analysis will be done only for Cut-off 1 analysis.

In addition, Kaplan-Meier curves by treatment will be used to present the time-dependent cumulative frequency and percentage of subjects reaching the first relapse; by-treatment Kaplan-Meier estimates (with 95% confidence interval) at both cut-off 1 and Cut-off 2 analyses will be obtained ([Section 2.14](#)).

MS relapse characteristics

For MS relapse characteristics, summary statistics will be presented. The proportion of patients hospitalized for relapse and the proportion of patients with severe relapses will be compared between treatment groups using a Chi-square test. For Cut-off 2 analysis, summary statistics will be presented by study period (up to Week 24 or thereafter).

MS relapse characteristics include severity, recovery, hospitalization, and steroid treatment. The severity of MS relapses will be derived according to the criteria presented in [Table 2-12](#). Severity will be derived for both types of relapses, confirmed and unconfirmed ones. It depends on the type of relapses which EDSS is used to derive severity:

- For confirmed relapses, the EDSS score used to confirm the relapse (as specified in Section 2.7.2) will be used to determine the severity.
- For unconfirmed relapses, all EDSS assessments taken within 30 days from the relapse start date and before the relapse end date will be checked among which the most severe case will

be selected to determine the severity. If no such EDSS assessment is available, the severity will be set to “missing EDSS”. If none of such EDSS assessments meets the mild, moderate or severe conditions, the severity will be set to “no worsening in EDSS”.

Table 2-12 Severity of MS relapse

Mild relapse	Moderate relapse	Severe relapse
EDSS increase of 0.5 point	EDSS increase of 1 or 2 points	Exceeding Moderate criteria
or	or	or
1 point FS change in one to three systems	2-point FS change in one or two systems	Exceeding Moderate criteria
	or	or
	1-point change in four or more systems	Exceeding Moderate criteria
Definition is based on the EDSS obtained to confirm the relapse as compared to the last EDSS (scheduled or unscheduled) taken in the absence of (confirmed or unconfirmed) relapse and prior to the current relapse. EDSS refers to total score; FS refers to functional score; all of the 7 functional scores are considered in this derivation.		

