These patients will be followed for a total of at least 36 weeks after study drug discontinuation (by 36 weeks the majority of patients are expected to have repleted their circulating B-cells, see Protocol Section 3.3).

A longer than 36 weeks of post-treatment Safety FU period will be required for patients who have not repleted their B-cells (i.e. B-cells not back to baseline value or to lower limit of normal (LLN) whichever comes first as determined by central lab) at 36 weeks.

These patients will continue to be followed with assessments every 12 weeks until their B-cell counts have repleted. To protect the study blind, the assessment of B-cell counts will be performed centrally and the Investigators and Sponsor study team will only be informed of whether or not continued follow-up is necessary.

Patients who have initiated therapy with another disease modifying/immunosuppressive therapy before the end of the 36-week follow-up will not be monitored beyond 36 weeks.

Figure 1-1 Study design

* Patients randomized to placebo in the Double-blind treatment period will receive ofatumumab 20 mg sc at Week 24, 25 and 26 as loading dose regimen. Patients randomized to ofatumumab in the Double-blind treatment period will receive ofatumumab 20 mg sc at Week 24 and the matching placebo sc at Week 25 and 26. In all patients, the extension part starts with the Week 24 injection.

** Patients who prematurely discontinue study drug or patients who do not enter the umbrella extension study will enter the Safety FU period following their EOS visits.

*** Umbrella extension study (planned) will be conducted under separate protocol.

Data cut-off 1 is defined as the date the last patient completes all the assessments for Week 24.

Data cut-off 2 is defined as the date the last patient completes all the assessments for Week 48.

Three types of analyses to be conducted are described in the SAP. They will be referred to in this document as Cut-off 1 analysis, Cut-off 2 analysis, and EOS analysis:

1. The Cut-off 1 analysis will be conducted for the Core part. Data up to the Week 24 (cut-off 1) will be used. Data from the safety FU period for patients who prematurely discontinued from study treatment before Week 24 will also be included. The analysis will be performed when the last patient has completed the double-blind loading dose period at Week 28. This analysis will be used in support of the registration of ofatumumab in Japan.

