2.1 Data analysis general information

Data will be analyzed by Novartis statistical and programming team according to the data analysis Section 9 of the study protocol which is available in Appendix 16.1.1 of the CSR. Important information is given in the following sections and details are provided, as applicable, in Appendix 16.1.9 of the CSR.

SAS (version 9.4 or higher) will be used for generating study outputs used for clinical reports.

Unless otherwise stated, summary tables/figures/listings will be on all subjects included in the population under consideration. Data will be summarized with respect to demographic and baseline disease characteristics, efficacy, and safety assessments.

The three analysis conducted at:

- Cut-off 1 (Core part data up to Week 24 visit),
- Cut-off 2 (all data obtained until the last patient completes all assessments up to Week 48 visit),
- Final, when the last patient completes the EOS visit or Safety FU period.

Each analysis will be conducted on all subject data available at the corresponding cut-off. Cut-off 2 and final *safety* analysis will include only each patient's assessments under ofatumumab treatment or during Safety FU.

In these analyses, data from Safety FU period will be analyzed separately if necessary.

The stratification factors, which are the number of Gd-enhanced T1 weighted lesions at baseline (0 or ≥ 1) and region (Japan or non-Japan), will be included in subgroup analysis where appropriate.

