2.1.1 General definitions

Study drug/treatment refers to the investigational drug Ofatumumab and placebo.

“Date of Cut-off 2” is expected as the date the last patient completes all assessments at Week 48 visit. If the last patient discontinues from the study prior to Week 48 visit, “date of Cut-off 2” is the last patient's last visit.

Date of first administration of study drug/treatment, or first date of study drug/treatment, is defined depending on the analysis purposes.

- For Cut-off 1 analysis and Cut-off 2 and final *efficacy* analysis, it refers to the date when the first dose of randomized treatment is administered.
- For Cut-off 2 and final *safety* analysis, it refers to the date when the first dose of ofatumumab is administered.

Date of last administration of study drug/treatment, or last date of study drug/treatment is defined by analysis time point.

- For Cut-off 1 analysis, it refers to the date when the last dose of randomized treatment is administered up to Week 24 visit.
- For Cut-off 2 analysis, it refers to the date when the last dose of treatment is administered up to the date of Cut-off 2.
- For final analysis, it refers to the date when the last dose of treatment is administered up to EOS visit.

Study day is defined as: if after first date of study drug, then (Study Day) = (Date) – (first date of study drug) +1; if before first date of study drug, then (Study Day) = (Date) – (first date of study drug); Study Day 1 is defined as the date of the first administration of study drug; there is no Study Day 0.

Duration of an event is calculated as (event end date) – (event start date) +1.

1 month is counted as 30 days unless otherwise specified.

Baseline is defined for each cut-off analysis.

- For Cut-off 1 analysis, and Cut-off 2 and final *efficacy* analysis, baseline is defined as the last non-missing result before or on the first date of study drug.
- For Cut-off 2 and final *safety* analysis, definition of baseline depends on each patient's treatment course in the study
 - For a patient continuously having ofatumumab across Core and Extension parts, baseline is defined as the last non-missing result before or on the first date of study drug.
 - For a patient switching the treatment from placebo to ofatumumab when entering the Extension part, baseline is defined as the dose date of ofatumumab at Week 24. *For analysis on vital signs*, the baseline is defined as *the pre-dose measurement* at Week 24.

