2.15 Analysis on the Extension part not mentioned in the previous sections

Switch effect from placebo to ofatumumab on the number of Gd-enhancing T1 lesions

Mean numbers of Gd-enhancing T1 lesions per scan, defined as

$(\text{total number of Gd-enhancing T1 lesions}) / (\text{total number of scans}),$

will be calculated by treatment and study period (up to Week 24, or thereafter).

Also, mean numbers of Gd-enhancing T1 lesions per scan will be summarized by region and study period.

In addition, mean numbers of Gd-enhancing T1 lesions per scan will be summarized by subgroup of home injection and study period.

Switch effect from placebo to ofatumumab on the number of new or enlarging T2 lesions

Annualized rate of new or enlarging T2 lesions, defined as

$(\text{total number of new or enlarging T2 lesions}) / (\text{total time of MRI assessment}),$

will be calculated by treatment and study period (up to Week 24, or thereafter).

For this calculation, each patient's number of new or enlarging T2 lesions will be relative to Week 24. In addition, definition of time of MRI assessment will depend on the study part:

- For the period up to Week 24, the time of MRI assessment will be defined as $(\text{Week 24 visit date}) - (\text{first dose date in the Core part}) + 1$ divided by 365.25.
- For the period after Week 24, the time of MRI assessment will be defined as $(\text{Week 48 visit date}) - (\text{Week 24 visit date})$ divided by 365.25. If Week 48 visit is not available, the time of MRI assessment will be defined as $(\text{last visit date up to Week 48}) - (\text{Week 24 visit date})$ divided by 365.25.

Switch effect from placebo to ofatumumab on the annualized relapse rate (ARR)

ARR (time-based and patient-based) will be summarized by study period (up to Week 24 or thereafter).

Here definition of time in study will depend on the study part:

- For the period up to Week 24, the time in study will be defined as (Week 24 visit date) – (first dose date in the Core part) + 1 divided by 365.25.
- For the period after Week 24, the time in study will be defined as (last visit date up to date of Cut-off 2) – (Week 24 visit date) divided by 365.25.

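### Relapse-rate time in study and relapse censoring run to an undefined cutoff point with no patient-level end date, so unobserved time can count as relapse-free

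*SAP*

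**What the plan says.** SAP 2.7.2 defines the ARR offset thus: the patient's "time in study for ARR at each cutoff will be calculated as (Cutoff point" minus the first dose date plus 1, divided by 365.25. For time to first confirmed relapse, patients without an event are handled the same way: "they are censored with censoring time as time in study at the corresponding cutoff point". Neither rule mentions withdrawal, loss to follow-up or a last assessment.

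The SAP uses Cut-off 1 in two senses:

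- **A calendar date.** SAP 1.1: "Data cut-off 1 is defined as the date the last patient completes all the assessments for Week 24".
- **A patient-level limit on the data.** SAP 1.1: "Data up to the Week 24 (cut-off 1) will be used". SAP 2.1: "Cut-off 1 (Core part data up to Week 24 visit". Several visit-window tables in SAP 2.1.2.1 also attach the Cut-off 1 label to the Week 24 window, whose target is Day 168 counted from the patient's own first dose.

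Cut-off 2 is a calendar date. Under SAP 2.1.1 it "is expected as the date the last patient completes all assessments at Week 48 visit".

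SAP 2.15, which summarizes ARR before and after the switch, uses patient-level end dates: "For the period up to Week 24, the time in study will be defined as (Week 24 visit date"), and after Week 24 "the time in study will be defined as (last visit date up to date of Cut-off 2"). Protocol 9.5.1.2 says that the offset is there to adjust for differing individual time in the study.

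**The concern.** An offset for time in study should measure the time over which a relapse could have been recorded for that patient. A common end point, with no patient-level stop, fails in two ways.

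First, a patient who leaves follow-up keeps accruing time, and that time enters the denominator as relapse-free. This amounts to imputing zero relapses, although SAP 2.7.4 says that missing data will not be imputed.

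Second, if the cutoff point at Cut-off 1 is the calendar date, everyone enrolled before the last patient also accrues time after Week 24, when placebo patients are receiving ofatumumab.

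The ARRs, their ratio, the hazard ratio and the Kaplan-Meier estimates are secondary efficacy results in a study meant to support registration in Japan. At Cut-off 2 the report could also carry two sets of ARRs on different denominators, one from SAP 2.7.2 and one from SAP 2.15.

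**Working it through.** **1. The plan's own figure.** SAP 3.2 assumes 60 patients randomized 2:1, ARRs of 0.40 and 0.16, dispersion 0.1 and 6 months of follow-up. It states a probability above 80% of observing a lower ARR on ofatumumab. Expected relapses are 20 × 0.40 × 0.5 = 4.0 on placebo and 40 × 0.16 × 0.5 = 3.2 on ofatumumab. The arm totals are negative binomial with sizes 20/0.1 = 200 and 40/0.1 = 400. Exact enumeration gives 83.6%, with ties a further 5.7%. With exactly 24 weeks it is 82.2%; with 18 and 36 patients it is 81.8%. The stated figure reproduces. It assumes the same fixed follow-up for every patient, so it does not test the time-in-study rule.

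**2. Which time enters on each reading.**

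| Reading | Completers | Patients who leave follow-up |
|---|---|---|
| Cut-off 1, calendar date | Time after Week 24 is added | Unobserved time to that date is added |
| Cut-off 1, own Week 24 | Correct | No Week 24 visit date exists; using Day 168 adds unobserved time |
| Cut-off 2, calendar date | Time after Week 24 is intended | Unobserved time to that date is added |

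**3. How much extra time the calendar reading could add.** The documents give no accrual duration. The Extension lasts 24 to 48 weeks and runs until the last patient has completed 24 weeks in it (Protocol 3.3), so planned entry spans about 48 − 24 = 24 weeks. Uniform entry over that span gives a mean of about 12 extra weeks. I take 12 as the assumption and 0 to 24 as the range.

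**4. Effect on ARR, with *e* = mean extra weeks.**

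- Only Core relapses counted: each ARR is multiplied by 24/(24 + *e*). The ratio stays 0.40.
- Relapses to the calendar date counted, with switched placebo patients relapsing at 0.16: placebo ARR = (0.40 × 24 + 0.16 × *e*)/(24 + *e*). The ofatumumab ARR stays 0.16.

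| *e* (weeks) | Core relapses only: placebo, ofatumumab | All relapses to the date: placebo, ratio |
|---|---|---|
| 0 | 0.40, 0.16 | 0.40, 0.40 |
| 6 | 0.32, 0.128 | 0.352, 0.45 |
| 12 | 0.267, 0.107 | 0.32, 0.50 |
| 24 | 0.20, 0.08 | 0.28, 0.57 |

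For *e* = 12, placebo: 0.40 × 24/36 = 0.267, and (9.6 + 1.92)/36 = 0.32.

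**5. Effect of unobserved time alone, taking Day 168 as the end.** Assume that lost patients miss half of the 24 weeks on average. If a fraction *d* is lost, the observed share of person-time is 1 − 0.5*d*, and the ARR shrinks by that factor.

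| Lost: placebo, ofatumumab | ARR: placebo, ofatumumab | Ratio |
|---|---|---|
| 10%, 10% | 0.38, 0.152 | 0.40 |
| 20%, 5% | 0.36, 0.156 | 0.43 |
| 5%, 20% | 0.39, 0.144 | 0.37 |

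Person-time in an arm is inflated by 1/0.95 − 1 = 5.3% with 10% lost and by 1/0.90 − 1 = 11% with 20% lost. The 10% is the dropout allowance in SAP 3; the 20% and 5% are assumptions. Read as dropout rates, the 5.3% and 11% are upper bounds, because they apply only to patients who leave follow-up altogether.

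**The case against.** The best defense is that Cut-off 1 is meant at patient level. SAP 1.1 and 2.1 limit that analysis to data up to Week 24, and the visit-window tables tie the label to Day 168. SAP 2.7.2 speaks of a point, whereas the SAP uses explicit date terms elsewhere when it wants a calendar date (the date of Cut-off 2, the end date of the Core part). Protocol 9.5.1.2 also says that the offset reflects individual time. A reader might infer that every patient's Cut-off 1 time runs to a calendar date. The documents do not establish that, since the calendar definition is one of two in use.

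A reader might also infer that every dropout adds unobserved time. That is too strong. Patients who stop treatment enter Safety Follow-up for at least 36 weeks, with relapse and EDSS assessed at each visit (Protocol Table 6-2), and SAP 1.1 includes their follow-up data at Cut-off 1. Only withdrawal of consent or true loss leaves a gap.

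Nor does the rule necessarily distort the treatment comparison. Equal inflation leaves the ARR ratio unchanged, and randomization gives no reason for entry timing to differ systematically by arm. If only Core relapses count, later censoring of completers changes neither the hazard ratio nor the Kaplan-Meier estimates through Week 24, because risk sets at the event times are the same. Much longer accrual would inflate the denominators further but would not fit the planned 24 to 48 week Extension, although a footnote to Protocol Table 6-1 allows for overrun. There are no key secondary objectives (SAP 2.6), and at Cut-off 2 no Cox model is fitted.

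All of this stands and narrows the point. It does not supply a patient-level end date for someone who leaves follow-up, and it does not reconcile SAP 2.7.2 with 2.15. SAP 2.15 is not a complete model either, because its rule gives no end date for a patient without a Week 24 visit.

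**Conclusion.** The time-in-study and censoring rule in SAP 2.7.2 is wrong as written. This is more than missing detail: a stated formula, applied literally, counts time in which no relapse could be recorded, against the offset's stated purpose and in conflict with SAP 2.15. Confidence is high on the missing patient-level end date and moderate on the calendar reading at Cut-off 1.

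The size depends on the reading and on assumptions that the documents cannot settle. If the cutoff point is the patient's own Week 24 and nobody is lost, there is no effect. From unobserved time alone the shift is small, even with the markedly unequal loss assumed above. On the calendar reading with 12 extra weeks, absolute ARRs fall by one third if only Core relapses count, and the ratio weakens from 0.40 to 0.50 if post-switch relapses count. The primary MRI analysis is untouched, because its offset is the number of scans.

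**What to change.** Replace the definition in SAP 2.7.2 with a patient-level end date:

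- **Cut-off 1:** the earlier of (a) the Week 24 visit date, before the first Extension dose, or Day 168 if there is no Week 24 visit, and (b) the last date with a relapse assessment, including Safety Follow-up.
- **Cut-off 2:** the earlier of the date of Cut-off 2 and the last date with a relapse assessment.

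The Day 168 clause is needed. Without it, a patient who stops early and enters Safety Follow-up has no Week 24 visit to cap the time, which could then run well past Week 24.

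Count only relapses with onset inside the same interval, use the same end date for Cox and Kaplan-Meier censoring, and align SAP 2.15 with it. Confirm which end date the Cut-off 1 programs used.

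The cost is a sentence or two in the SAP and a check of the programs, with a rerun of the relapse outputs only if they used another date. No new data are needed.
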